KDHRC will conduct a two-group, randomized pretest/posttest feasibility evaluation study (henceforth, study) to explore the extent to which the prototype changes CHWs' knowledge, skills, attitudes, self-efficacy, and intentions to provide optimal care and resources to postpartum minority mothers. The study will consist of pretest and posttest surveys and videos with four lessons (treatment) or a waitlist control (control), pending Institutional Review Board (IRB) approval. The participants in the study are CHWs. KDHRC has contracted with community-based organizations (CBOs) to assist with CHW referral to the study.

¹ KDHRC internal files will introduce the course as ENCORE, then include a note about the name change.

² CHWs include community health workers (CHWs), community health representatives (CHRs), lay health workers, and other titles.

This protocol describes the procedures for the study.

Responsible Parties

[name], is the principal investigator with oversite of the project. [name], KDHRC senior research scientist, is the project director. [name] and [name], KDHRC research assistants, will program online surveys, send communications to participants, and track participants through the study.

Specifically, KDHRC will:

- Contract and share study materials with CBOs (referral subcontractors) to refer participants.
- Share study materials with KDHRC's CHW Panel. The Panel includes CHWs who have signed up to receive notifications about research study opportunities.
- Program and manage the online screener, consent forms, pretest survey, and posttest survey.
- Send follow-up communications to consented participants.
- Manage, clean, and analyze data.
- Manage incentive distribution.
- Report on study findings.

KDHRC has contracted with CBOs with CHWs who serve minority women to be the referral subcontractors. To be eligible, each CBO must demonstrate organization stability and their capacity to participate in the study by having:

- (1) Federal nonprofit tax-exempt status under Section 501(c)(3) of the Internal Revenue Code.
- (2) Internet access to share the referral materials with their network of CHWs.
- (3) At least one active program that conducts health outreach minority women with a minimum of 15 active CHWs on staff (paid or volunteer).
- (4) A dedicated point of contact (POC) who will participate in a kick-off call with KDHRC and oversee the study at their CBO.

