CBOs will refer potential participants in their networks, including potential participants within their CBOs, by sharing KDHRC-developed and IRB-approved referral materials (e.g., email template, flyer) through email (e.g., listservs) and message boards. KDHRC will also share study materials with KDHRC's CHW Panel. The referral materials will contain the link to the screener, information on the time commitment, and instructions to contact KDHRC with questions. The study will include up to 160 CHWs nationwide (80 treatment, 80 control) from up to 12 CBOs and the KDHRC CHW Panel. Although CBOs will refer participants and may have access to potential participant information (e.g., name, email address) from their listservs, CBOs will not have knowledge of who actually serves as study participants and will not have access to enrolled participants' data. KDHRC will remind participants that participation in the study is completely voluntary, and that his or her participation is no way tied to his or her position at and/or relationship with the CBO that shared referral materials with him or her.

Eligibility criteria for CHWs include:

- Must be at least 18 years old.
- Must self-identify as a community health worker (CHW).
- Must live in the United States.
- Must conduct outreach to minority women.
- Must have six months of field experience. KDHRC defines "field experience" as conducting outreach activities in their community, for example, working with clients in a clinic, conducting home visits, or educating clients at health fairs or community events.

- Must be an active CHW. KDHRC defines "active" as conducting outreach activities, such as working with clients in a clinic, conducting home visits, or educating clients at health fairs or community events, in the last six months.
- Must have Internet access either at home or at work to access the lessons and/or online surveys.

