CHWs will be referred to the study through the CBOs or via KDHRC's CHW Panel. Materials will direct interested CHWs to an online link for screening and informed consent. KDHRC will share receive referral links with participants to refer colleagues who may be interested in research studies. Each referral link will include a specific code that links to the referring CHW. Only KDHRC researchers will have access to this code. Referring CHWs will not know if referred CHWs access and complete the referral link. Referred CHWs information will be kept confidential. Referral links will open in a separate form for referred CHWs to sign up for the KDHRC CHW Panel. Depending upon the referral completion timeline, referred CHWs may receive information about the MOMS Postpartum study via CHW Panel communications.

KDHRC will confirm consent for each participant and after confirming consent, KDHRC will randomize each participant with completed consent into the treatment or control group using a 1:1 randomization. KDHRC will alternate assigning each participant with completed consent to the treatment group or the control group. Then, KDHRC will send each participant the link to the online pretest survey. After completing the pretest survey, each treatment group participant will receive access to the prototype. Specifically, the participants in the treatment group will receive a link to a KDHRC Teachable School³ where they will access the lessons. Participants can access the lessons by computer or smart phone. The control group will receive no intervention. Each participant will receive the posttest survey no more than two weeks after completing the pretest survey.

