Participants in both the treatment group and the control group will receive a \$25 e-gift card (Amazon or Walmart) incentive after completing the pretest survey, and a \$25 e-gift card (Amazon or Walmart) incentive after completing the posttest survey for a total of up to \$50 in e-gift card incentives (Amazon or Walmart). Participants in the treatment group will receive an additional \$25 incentive for completing the prototype lessons. KDHRC calculated this amount based on the length of the surveys and amount of time required to review the treatment and control materials. This incentive amount is comparable to incentives KDHRC has successfully used for feasibility evaluation studies. Inadequate compensation for time spent participating in a study may result in a difficult and lengthy recruitment process and/or participants who agree to participate and then drop out early. The use of incentives treats participants justly and with respect by recognizing and acknowledging the effort they expend to participate, but also respects that they may have other responsibilities such as childcare or employment.

Upon completing and submitting the screener, participants will receive the link to the consent form via email. A KDHRC researcher will send approximately three reminders (email, phone, text) per week for up to two weeks to each eligible participant to complete the consent form.

³ Teachable is a secure online learning platform. Users will sign up for a free account from Teachable and then receive free access to the MOMS Postpartum lessons.

Upon completing and submitting the consent form to participate, each participant will be randomly assigned to either the treatment group or the control group. Then, KDHRC will send each participant the link to the online pretest survey. Participants will have up to one week to complete the pretest survey. A KDHRC researcher will send approximately three reminders (email, phone, text) per week to each consented participant to complete the pretest survey.

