KDHRC will email the treatment group participants the information to access the lessons. When each participant accesses the lessons for the first time, the participant will be prompted to create a user ID and password. Participants in the treatment group will have up to two weeks to complete the lessons. Participants in the control group receive no intervention. KDHRC will send one reminder (email or phone) per week to participants to promote continued engagement with the study (e.g., remind treatment participants to complete the modules; remind control participants of the date when they will receive their posttest survey).

Then, no more than two weeks after pretest completion, KDHRC will email all participants the links and instructions for posttest survey completion. Each participant will have up to one week to complete the posttest survey. A KDHRC researcher will send approximately three reminders (email, phone, text) per week to each consented participant with a completed pretest survey to complete the posttest survey.

The links to the pretest and posttest surveys will be used to collect participant data, therefore only KDHRC staff will have access to raw data. Each survey will take no more than 30 minutes to complete.

Analysis

After completion of the study, KDHRC will download the raw data from Alchemer into encrypted Excel spreadsheets. KDHRC will import the data into STATA, a quantitative statistical software, to analyze and assess the extent to which the prototype increases CHWs' knowledge, skills, attitudes, self-efficacy, and intentions to provide support to postpartum minority women.

Timeline

The study will begin immediately upon obtaining IRB approval. All data collection will conclude by April 30, 2025.

DATA COLLECTION

KDHRC will collect quantitative data from up to 160 CHWs (80 CHWs per group) through online surveys only. If KDHRC encounters low participant numbers and/or high attrition rates, then KDHRC will contract with additional CBOs and utilize additional referral methods (e.g., social media) to reach additional participants. This will not impact the rights of or risk to study participants.

Identifying Information

CBOs will not have access to enrolled participants' survey responses. Although CBOs will refer participants and may have access to potential participant information (e.g., name, email address)

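### The study is called randomized 1:1, but the only assignment rule is alternation, and nothing hides the next arm from the staff who process consents

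*Combined protocol and SAP*

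**What the plan says.** Background (Purpose of Research) describes a "two-group, randomized pretest/posttest feasibility evaluation study". Research Design (Approach) states that "KDHRC will confirm consent for each participant and after confirming consent, KDHRC will randomize each participant with completed consent" to one of the two groups "using a 1:1 randomization". The next sentence gives the method: "KDHRC will alternate assigning each participant with completed consent to the treatment group or the control group". Later in the same section the protocol says "Upon completing and submitting the consent form to participate, each participant will be randomly assigned to either the treatment group or the control group", without naming a mechanism.

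The same section has a KDHRC researcher send "approximately three reminders (email, phone, text) per week for up to two weeks to each eligible participant to complete the consent form". Responsible Parties gives the research assistants participant communications and tracking, and describes no separate allocation role. The nearest thing to concealment concerns the referring organizations: "CBOs will not have knowledge of who actually serves as study participants". The target is up to 160 CHWs, 80 per arm.

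On analysis, the plan says only that "KDHRC will import the data into STATA, a quantitative statistical software, to analyze and assess the extent to which the prototype increases" the listed outcomes. It names no test and no use of the pretest score.

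**The concern.** Randomization and alternation are different procedures, and the protocol asserts the first while specifying the second. The study question is how far exposure to the prototype raises the outcomes. Because controls receive nothing, the answer rests on the comparison between arms, and therefore on how the arms were formed.

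Under alternation, whoever handles consents knows the next arm. KDHRC does the chasing, the confirming and the assigning, and the protocol does not say what fixes the order of the queue. A person who knows the next slot is treatment could confirm one waiting consent before another or, less directly, press one CHW sooner than another. Several outcomes (attitudes, self-efficacy, intentions) come from survey answers, so a difference in engagement between arms could plausibly shift them. Even if nobody does this, the label would be wrong in every report, and for later users of the public data deposit.

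**Working it through.** **1. What the stated rule implies.** Inputs from Approach: alternation; N = 160; 80 per arm. Strict alternation over 160 gives 80/80, matching the stated split. Only two sequences are possible (treatment first or control first). If the first arm is known, 159 of 159 later assignments are determined. If it is unknown, the expected share guessed correctly is (159 + 0.5)/160 = 99.7%.

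**2. Comparison with random methods.** Share of assignments guessed correctly by the best guesser who sees all past assignments (block sizes are illustrative, not from the protocol):

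| Method | Correct guesses |
|---|---|
| Alternation, first arm known | 100% |
| Simple randomization | 50% |
| Blocks of 4, size known (enumeration) | 17/24 = 71% |
| Blocks of 6, size known (enumeration) | 41/60 = 68% |
| Blocks of 4 and 6 mixed at random, sizes unknown (4,000 simulated sequences) | about 69% |

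Blocking therefore reduces predictability but does not remove it, so concealment matters as well as the sequence.

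**3. What steering could do (illustration only).** None of these assumptions is in the documents:

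- The 160 CHWs arrive as 80 consecutive pairs.
- Engagement correlates ρ with both pretest and posttest.
- In a fraction f of pairs, the more engaged CHW is placed in treatment.
- There is no true effect; tests are two-sided at 0.05.

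The expected gap between the larger and smaller of two standard normal values is 2/√π = 1.128, so the posttest bias is f × ρ × 1.128 SD. Half of the steered pairs already fall the desired way, so actual swaps = f × 80/2.

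For ρ = 0.5:
- f = 10%: 0.10 × 0.5 × 1.128 = 0.056 SD; 4 swaps
- f = 25%: 0.25 × 0.5 × 1.128 = 0.141 SD; 10 swaps
- f = 50%: 0.50 × 0.5 × 1.128 = 0.282 SD; 20 swaps

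Hand check on rejection: the standard error of the difference is about √(2/80) = 0.158 SD. At f = 50% the shift is 0.282/0.158 = 1.78 standard errors, and Φ(1.78 − 1.96) = Φ(−0.18) = 0.43. Simulation (20,000 replicates) agrees:

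| Analysis | f = 10% | f = 25% | f = 50% |
|---|---|---|---|
| Unadjusted posttest, ρ = 0.5: bias (SD) / null rejection | 0.06 / 6% | 0.14 / 14% | 0.28 / 43% |
| Unadjusted posttest, ρ = 0.3 | 0.03 / 5% | 0.08 / 8% | 0.17 / 19% |
| Adjusted for pretest, ρ = 0.5, pre-post correlation 0.5 | 0.03 / 5% | 0.07 / 8% | 0.14 / 18% |
| Adjusted for pretest, ρ = 0.5, pre-post correlation 0.7 | 0.02 / 5% | 0.04 / 6% | 0.09 / 11% |
| Change score, ρ = 0.5, pre-post correlation 0.5 | 0.00 / 5% | 0.00 / 5% | 0.00 / 5% |

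With f = 0, every analysis rejects at about 5%.

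**The case against.** The best reply accepts the contradiction and disputes the harm.

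- **Safeguards.** Screening and consent are online, assignment follows consent, staff have no stated discretion to refuse an eligible consented CHW, and the referring organizations do not learn who enrols. This stands and narrows the opening to the order of confirmation and the timing of consent. None of it hides the next arm from KDHRC.
- **The illustration is harsh.** It assumes that staff rank engagement perfectly and that two consents are open to reordering at once. Assignment precedes the pretest, so staff have no outcome data. If their perception correlates only 0.5 with engagement (also an assumption), unadjusted rejection at f = 25% and 50% falls to about 7% and 14%. This stands; the values of f have no source.
- **Change scores remove the bias.** In this model they do, because engagement affects pretest and posttest equally, and the protocol does plan to match the two surveys for each participant. But the Analysis section commits to no such test, and the bias would return if engagement predicted gain.
- **Order of assignment.** The two accounts, after KDHRC confirms consent and upon submission, can be read as one sequence: submit, confirm, assign. That is fair. What is missing is a rule for the order in which confirmed consents are assigned.
- **It is an exploratory feasibility study.** True, and no alpha, power or confirmatory hypothesis is stated. That lowers the stakes of any bias, but it does not make alternation random.

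**Conclusion.** The concern holds and should be fixed before the study is run or reported. The core of it needs no simulation: the protocol claims random assignment in three places, its only operative rule is deterministic, and no concealment from KDHRC staff is described. This assumes the plain reading of one alternating queue; separate queues per organization would be just as predictable within each queue.

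The size of any resulting bias cannot be known from the documents. With no steering it is nil. Under the illustrative assumptions it runs from nothing (change scores) to 0.28 SD and 43% null rejection (unadjusted posttest, half of pairs steered, perfect ranking of engagement). The upper end should be read as a bound on an unfavourable scenario, not as an estimate.

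**What to change.** Replace the alternation sentence with text along these lines:

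> A computer-generated 1:1 sequence in permuted blocks of randomly varying size (4 and 6) is prepared before enrolment and kept concealed, either within an automated system or by a KDHRC team member who neither chases nor confirms consents. Consents are taken in order of submission time, and each arm is revealed only after the consent is logged.

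The separation of roles is needed because someone who sees all past assignments can still guess about 69% of mixed-block assignments. Arm sizes would differ by at most 3 at any stopping point (half of a block of 6), so the 80/80 target does not require alternation. Simple randomization would also cure the label and the predictability, at the price of less equal arms: in simulation, 95% of sequences put each arm within 12 of 80.

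If alternation is kept or has already been used, remove the claims of randomization from Purpose of Research, from both places in Approach and from all reports; describe the study as quasi-randomized; and report how many assignments departed from consent-submission order.

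Cost: one protocol paragraph, a short script, and an IRB amendment if approval has already been given. No extra participants. It needs an automated list or one role split among the principal investigator, project director and two research assistants; the protocol does not say whether any of them is free of consent work. Relabelling costs only wording, but gives up the randomized claim.

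### Participants are assigned by alternation at consent, before the pretest, although nothing differs by arm until after it; assigning at pretest receipt from a concealed random sequence is a cheap improvement

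*Combined protocol and SAP*

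**What the plan says.** All references are to the combined protocol and SAP.

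- **Time of assignment** (RESEARCH DESIGN, Approach): "Upon completing and submitting the consent form to participate, each participant will be randomly assigned to either the treatment group or the control group". The pretest link is sent next, and participants have up to one week to complete the survey.
- **Method** (Approach): allocation is called 1:1 randomization, but the procedure given is "KDHRC will alternate assigning each participant with completed consent to the treatment group or the control group".
- **First arm-specific step** (Approach): "After completing the pretest survey, each treatment group participant will receive access to the prototype". Weekly messages that differ by arm come later still: "remind treatment participants to complete the modules; remind control participants of the date when they will receive their posttest survey".
- **Before the pretest** (Approach): one reminder rule covers everyone, "A KDHRC researcher will send approximately three reminders (email, phone, text) per week to each consented participant to complete the pretest survey", and both arms are paid the same $25.
- **Posttest** (Approach): "Each participant will receive the posttest survey no more than two weeks after completing the pretest survey". Posttest reminders go to "each consented participant with a completed pretest survey to complete the posttest survey".
- **Matching** (DATA COLLECTION, Identifying Information): at the posttest, participants enter a self-created ID and select that the pretest is already done. The platform then builds one matched pretest and posttest record per person. Names are not linked to responses.
- **Numbers**: up to 160 CHWs, 80 per group (Approach and DATA COLLECTION). BACKGROUND, Terminology, defines participants as CHWs who have completed consent. No dropout rate is given, and the Analysis section defines no analysis set.

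**The concern.** Two features of the allocation step weaken the comparison, and the plan describes no benefit from either.

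First, under alternation anyone who knows the last assignment knows the next one. The organisation that makes the assignments also chases consents, and no concealment is described.

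Second, assignment comes up to a week before any step that needs it. A consenter who does not return the pretest has been assigned but has no described route to outcome data. The groups compared are then those who stayed after assignment, not those assigned. If the two arms lose different numbers or different kinds of people at this stage, part of the observed difference reflects who returned the pretest and not the course.

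**Working it through.** **1. Order of steps.** The sequence is consent, assignment, pretest link, pretest (up to one week), lesson access for the treatment arm, posttest. Nothing described between assignment and pretest return depends on the arm.

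**2. What happens to a consenter with no pretest.** The posttest date is counted from pretest completion, so it is undefined for this person. The posttest reminder list requires a completed pretest. The gateway asks the person to confirm a completed pretest, and the dataset is matched pretest and posttest. Exclusion is therefore a strong inference, though not a stated rule.

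**3. The plan's own figure.** 80 + 80 = 160 agrees. No alpha, power, effect size, SD or dropout rate is given, so 160 cannot be derived. Every rate, deficit, correlation and test level below is an assumption.

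**4. Bias formula.** Let r be the proportion in an arm who do not return the pretest, and d the amount in SD by which they would score below returners. The mean of the returners exceeds the mean of all assigned by r × d. The bias in the arm difference is r1 × d1 − r2 × d2 in absolute value. It is zero when both r and d are the same in the two arms.

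**5. Unequal rates, same d, unadjusted posttest means, 80 assigned per arm.** With b the bias, the two-sided 5% error rate is Φ(−1.96 + b/SE) + Φ(−1.96 − b/SE).

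| Non-return | Remaining | SE | d | Bias (SD) | Error rate |
|---|---|---|---|---|---|
| 10% vs 15% | 72 vs 68 | √(1/72 + 1/68) = 0.1691 | 0.25 | 0.05 × 0.25 = 0.0125 | 5.1% |
| 10% vs 15% | 72 vs 68 | 0.1691 | 0.5 | 0.05 × 0.5 = 0.025 | 5.3% |
| 10% vs 20% | 72 vs 64 | √(1/72 + 1/64) = 0.1718 | 0.25 | 0.10 × 0.25 = 0.025 | 5.2% |
| 10% vs 20% | 72 vs 64 | 0.1718 | 0.5 | 0.10 × 0.5 = 0.05 | 6.0% |

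**6. With baseline adjustment, last row.** The SE becomes 0.1718 × √(1 − ρ²), which is 0.1488 at ρ = 0.5 and 0.1227 at ρ = 0.7.
- Same deficit at both surveys: bias is 0.05 × (1 − ρ). At ρ = 0.5 this is 0.025 SD, with an error rate of 5.3%. At ρ = 0.7 it is 0.015 SD. A change score removes it.
- Deficit at the posttest only: bias stays at 0.05 SD, and the smaller SE raises the error rate to 6.3% (ρ = 0.5) or 6.9% (ρ = 0.7).

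**7. Equal rates, different skippers.** With 20% non-return in both arms and deficits of 0.5 and 0.25 SD, the bias is 0.20 × 0.5 − 0.20 × 0.25 = 0.05 SD. Equal rates alone do not guarantee zero bias, so the values above are examples and not limits.

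**8. Consents needed for 160 people with a pretest.** 160/0.95 gives 169, 160/0.90 gives 178 and 160/0.80 gives 200. The number is the same whichever step comes first.

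**9. Arm sizes under the fix.** Simple randomisation of 160 has an SD of √160 = 12.6 for the arm-size difference, so a 95% range of about ±25. Blocking avoids this. For example, 16 blocks of 4 and 16 of 6 give 64 + 96 = 160, exactly 80 per arm, with a difference of at most 3 if recruitment stops early.

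**The case against.** The strongest reply is that no mechanism for arm-related skipping is documented. Before the pretest both arms receive the same link, the same reminder rule and the same $25 "incentive after completing the pretest survey". Nothing says that participants learn their arm by then. This stands, and it limits the point. A reader might infer that reminder staff know the arm while chasing pretests, because the later weekly messages differ by arm. The documents show only that the senders know it after the pretest, not when they learn it.

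A second reply is that exclusion of skippers is nowhere stated, and one sentence in Approach has the posttest link emailed to all participants. That same sentence counts the time from pretest completion, so it gives no date for someone without one. Exclusion remains very probable but inferred.

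Third, the effect is small, the study is an exploratory feasibility evaluation, and the plainly arm-dependent burden (four lessons in one arm only) falls after the pretest. All of this is correct. It sets the weight of the point but supplies no reason for the present order.

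Fourth, alternation and timing are separable: curing one does not cure the other. That is so. The figures above measure timing only and say nothing about the size of harm from predictable allocation. Both are settled by rewriting the same two sentences.

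A reader might also infer that the present order costs power. It does not: moving assignment makes nobody complete the pretest, and chance imbalance is negligible. For 128 people, a split of 69 to 59 instead of 64 to 64 raises the SE by a factor of 0.1773/0.1768 = 1.003.

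**Conclusion.** The point holds as a cheap improvement. Assignment at consent, by a predictable rule, before any arm-specific step is explicit in the text. Loss of pretest skippers from the comparison after assignment is very probable.

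The documents do not support the stronger conclusion that the comparison will be biased. Expected bias is zero if skipping is unrelated to arm in both rate and type of skipper. Under the assumed 10% versus 20% non-return and deficits of 0.25 to 0.5 SD, it is 0.025 to 0.05 SD. A 5% test then has an error rate of 5.2% to 6.0% unadjusted. At the larger deficit with baseline adjustment, the rate is 5.3% (ρ = 0.5, same deficit at both surveys) or 6.3% to 6.9% (posttest-only deficit, ρ = 0.5 to 0.7). The case for change rests on avoidability, not on size.

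**What to change.** In RESEARCH DESIGN, Approach, replace both statements of assignment at consent, and the alternation sentence, with wording such as: *Each participant is assigned 1:1 promptly on receipt of the completed pretest survey, from a pre-generated random sequence in permuted blocks of varying size. Upcoming assignments are concealed from staff who recruit participants or send reminders. The arm is recorded against the study ID, and treatment participants are then sent lesson access.*

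- Only upcoming assignments need concealing. Staff may know a participant's arm once it is assigned, as the weekly messages require.
- State how the arm is recorded against the ID consistently with Identifying Information, where IDs are self-created and names are not linked to responses.
- Count the 80 per group from assignment, and report how many consented but did not return the pretest.

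**Cost.** The sequence must be generated and held separately. KDHRC must already detect each pretest completion to pay the incentive and release lessons. The participant timeline stays at 1 + 2 + 1 = 4 weeks at most. Assignment must be prompt, because the posttest clock runs from pretest completion and delay shortens lesson time.

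The effect on recruitment depends on what 160 means. If it means people with data, about 169 to 200 consents are needed at an assumed 5% to 20% non-return, under either order. If it means consenters, there are two options. The sponsor can keep the cap and accept fewer than 160 assigned. Otherwise it should state the 9 to 40 extra consents and their incentives, and check them against the April 30, 2025 end of data collection. At 20% non-return that adds 160 − 128 = 32 pretest completers and at most 32 × $50 + 16 × $25 = $2,000.

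The change does not affect loss between pretest and posttest.

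### Nothing closes the treatment arm's lesson access while the online posttest is open, so knowledge items can be answered with the lessons to hand in that arm only

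*Combined protocol and SAP*

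**What the plan says.** The Data Collection section says that data come "through online surveys only". The last paragraphs of Research Design, Approach add "Each survey will take no more than 30 minutes to complete" and "Each participant will have up to one week to complete the posttest survey". No supervision, timer or single-sitting rule is described.

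Only the treatment arm is given the lessons. Approach says "After completing the pretest survey, each treatment group participant will receive access to the prototype", and that "the participants in the treatment group will receive a link to a KDHRC Teachable School". Footnote 3 describes the account: "Users will sign up for a free account from Teachable and then receive free access to the MOMS Postpartum lessons". Controls get no intervention during the study; Purpose of Research calls them a waitlist control but gives no date for releasing the lessons to them.

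Two timing rules stand close together in Approach: "Participants in the treatment group will have up to two weeks to complete the lessons" and "Then, no more than two weeks after pretest completion, KDHRC will email all participants the links and instructions for posttest survey completion". The Identifying Information section separately places the posttest email after the intervention period is over. None of these sections says that lesson access is closed, suspended or allowed to expire.

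**The concern.** The research question asks whether exposure to the prototype increases knowledge, among other things. A knowledge item with a factual answer measures learning only if the respondent answers without the source in front of them. Under the protocol as written, a treatment participant can have the lessons open while answering, and a control has not been given them. Look-up of lesson content would therefore raise scores in one arm and push the difference towards the prototype.

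The pretest cannot correct this. Lesson access starts only after the pretest, so a baseline score carries no information about later look-up. Nor does the plan provide for correction afterwards. The Analysis section contains no check on look-up, and Identifying Information says that names and other identifiers are not linked to survey responses, so matching lesson-account activity to answers is not foreseen. Prevention is the practical route.

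**Working it through.** The plan states no figure on this point: no effect size, SD, power or expected score. There is nothing to reproduce, so the check has two parts: the timing that the documents allow, and an illustration of scale on assumed values.

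**Timing.** Day 0 is pretest completion. Inputs from Approach: lessons to be completed within 14 days, posttest sent on day s with s at most 14, posttest open up to 7 days. Same-day lesson access is an assumption. Overlap = min(14, s + 7) − s, not below 0.

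- s = 7: posttest closes on day 14; overlap 14 − 7 = 7 days.
- s = 10: closes on day 17; overlap 14 − 10 = 4 days.
- s = 14: closes on day 21; overlap 14 − 14 = 0 days.

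For sends before day 14, the protocol itself gives treatment participants lesson time while the posttest is open. If access is granted d days after the pretest, the lesson window runs to day 14 + d, and even the latest permitted send overlaps it by d days (up to the 7-day posttest window). With no overlap at all, no text stops the account from working through day 21.

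**Scale in percentage points.** All inputs are assumed: unaided treatment score 60%, a share of the arm that looks up, and the share of otherwise missed items that they correct. Inflation of the arm mean = (share looking up) × (share of missed items corrected) × (100 − 60).

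- Low: 0.10 × 0.25 × 40 = 1 point.
- Middle: 0.25 × 0.50 × 40 = 5 points.
- High: 0.50 × 0.50 × 40 = 10 points.

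**Scale as a false finding.** Inputs: 80 per arm from Approach (a ceiling, here taken as all analysed); assumed two-sided alpha 0.05, SD 1 and no true learning effect. Bias b = (share looking up) × (gain in SD). The chance of a significant result favouring treatment is Φ(b / √(2/80) − 1.96), with √(2/80) = 0.158.

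| Share looking up | Gain 1 SD: bias, chance | Gain 0.5 SD: bias, chance |
|---|---|---|
| 10% | 0.10, 9.2% | 0.05, 5.0% |
| 20% | 0.20, 24.4% | 0.10, 9.2% |
| 30% | 0.30, 47.5% | 0.15, 15.6% |
| 50% | 0.50, 88.5% | 0.25, 35.2% |

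With no look-up the chance in that direction is 2.5%. For comparison, 80 per arm detects (1.96 + 0.84) × 0.158 = 0.44 SD with 80% power.

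**The case against.** The strongest reply is that the documents are silent here, and silence is not permission. The posttest email carries instructions that are not in the supplied text, and they may tell participants not to consult anything. Identifying Information treats the intervention as a bounded period that precedes the posttest, so the two-week lesson limit might be meant as an end of access. Incentives are paid for completing surveys and lessons, not for scores. The lessons are videos of 20 to 30 minutes each, awkward to search during a survey of at most 30 minutes. Both arms can use other online sources, and the study is an exploratory feasibility evaluation.

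Much of this stands. A reader might infer that the knowledge test *is* open-book; the documents neither allow nor forbid look-up, so they support only that it *can* be. The asymmetry concerns lesson content: other sources are open to both arms, and controls might see lessons through colleagues. The look-up share and gain are unknown and may be small.

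Three things do not fall away. Placing the posttest after the intervention period orders the emails; it does not close an account. The completion limit is stated as time to finish, and the send rule allows the posttest inside it. An instruction, if there is one, would still leave the lessons available to one arm.

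**Conclusion.** The point holds in a limited form. The posttest is online with no described supervision, stays open for up to a week, and no end is set to the treatment arm's lesson access. A between-arm difference in knowledge may therefore mix look-up with learning, with look-up of lesson content favouring the prototype. The size cannot be computed from the documents; the figures above show only that modest look-up could matter at 80 per arm.

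Two stronger readings should be resisted. A reader might conclude that the study could say nothing about knowledge; the supported claim is that the plan gives no means of separating the two sources of a difference. A reader might also take knowledge as the main outcome because it is listed first. It is one of five domains and none is named primary. Self-reported attitudes, self-efficacy and intentions are much less exposed to look-up.

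The change is worth making before the study runs, because it is cheap and pretest adjustment cannot do the same job.

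**What to change.** 1. Reconcile the posttest send time in Approach with the two-week lesson window and with the statement in Identifying Information, so that each treatment participant's posttest opens only once that participant's lesson period has ended. Apply the same day count to controls. This comes first: suspending access under the present send rule could cut into the lesson window and affect the $25 lesson incentive.
2. State in Approach that KDHRC suspends the participant's access to its Teachable School from posttest opening until submission or close of the posttest window, and then restores it.
3. Show one identical instruction in both arms on the first posttest page: answer without consulting course or other materials.

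Optionally, add a closing item asking whether any materials were consulted, and report it descriptively by arm. An analysis that drops those who answer yes should be labelled exploratory. It conditions on behaviour after allocation that can differ by arm, relies on honest self-report, may remove the most engaged treatment participants, and does not isolate learning.

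The cost is an access setting managed per participant, one instruction and, if wanted, one item. KDHRC already tracks completion for reminders and incentives. The downside is that treatment participants cannot revisit lessons while their posttest is open.
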